6.5.4 Laboratory evaluations

Laboratory samples will be analyzed locally. Values outside the normal ranges and notable values should be flagged on the report. It is the responsibility of the investigator to review all laboratory results and make an assessment of whether an abnormal or notable value is clinically significant, whether additional evaluations should be performed as judged appropriate, and whether the patient may continue in the trial. Sample collection should be conducted according to the standards and requirements of the local laboratory.

- Laboratory values that exceed the boundaries of a notable laboratory abnormality (refer to [Appendix 1](#)) must be commented on by the investigator in the source documents and additional laboratory evaluations should be performed, as judged appropriate by the investigator.
- If the laboratory abnormality induces clinical signs or symptoms, or requires therapeutic intervention, and satisfies the criteria defined in [Section 7.1](#), then the diagnosis or medical condition must be entered on the AEs page of the patient's eCRF and any treatment necessary should be documented. If the laboratory abnormality is the primary reason for an unforeseen hospitalization or otherwise fulfills the seriousness category of an AE, then the procedure for rapid notification of SAEs must be followed.
- Likewise, if the laboratory abnormality leads to discontinuation of the study drug, the patient must be followed until the abnormality resolves or until it is judged to be permanent. This investigation may include continued monitoring by repeat laboratory

testing or by performing additional laboratory tests as deemed necessary by the investigator or the Sponsor's medical monitor.

Clinically notable laboratory findings are defined in [Appendix 1](#).

Full laboratory clinical chemistry ([Table 6-2](#)) will be performed locally at Visit 1 and abbreviated laboratory evaluations (sodium, potassium, creatinine) will be performed locally at Visits 2, 3, 4, 7 and 9. At Visits 5, 6 and 8 local labs will include sodium, potassium, creatinine, ALT, AST, alkaline phosphatase and total bilirubin.

Full laboratory tests will include the following:

Table 6-2 Full laboratory evaluations

Biochemistry
Sodium
Potassium
BUN
Creatinine
Total bilirubin
AST
ALT
γ GT
Alkaline phosphatase
Creatine phosphokinase (CPK)
Uric acid
Total protein
Albumin

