7.3 Liver safety monitoring

To ensure patient safety and enhance reliability in determining the hepatotoxic potential of an investigational drug, a standardized process for identification, monitoring and evaluation of liver events has to be followed.

Liver events are divided into two categories:

- Liver events of special interest (AESI) which consist of LFTs elevations
- Medically significant liver events which are considered as serious adverse events (SAEs) and which consist of marked elevations of LFTs and / or pre-specified adverse events.

Please refer to [Table 14-1](#) in Appendix 2 for complete definitions of liver events.

Any liver event which meets the criteria for "**medically significant**" event as outlined in [Table 14-1](#) of Appendix 2 should follow the **standard procedures for SAE reporting** as described in [Section 7.2.2](#).

Every liver event as defined in [Table 14-1](#) of Appendix 2 should be followed up by the investigator or designated personal at the trial site as summarized below. Detailed information is outlined in [Table 14-2](#) in Appendix 2.

- Repeating the LFT to confirm elevation as appropriate
- Discontinuation of LCZ696 if appropriate
- Hospitalization of the patient if appropriate

- A causality assessment of the liver event via exclusion of alternative causes (e.g., disease, co-medications)
- An investigation of the liver event which needs to be followed until resolution.

These investigations can include serology tests, imaging and pathology assessments, hepatologist's consultancy, based on the investigator's discretion. All follow-up information, and the procedures performed should be recorded on appropriate CRF pages, including the liver event overview CRF pages.

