9.4 Analysis of the primary variable(s)

The primary objective of this study is to evaluate the safety and tolerability of LCZ696 and to provide heart failure patients from PARADIGM-HF receiving open-label investigational drug. The primary assessment for safety will be based on the frequency of adverse events (AE) including:

- Overall AEs
- Serious adverse events (SAEs)
- adverse events of special interest (AESI), i.e., hypotension, hyperkalemia, or renal dysfunction
- Angioedema/angioedema-like events
- Deaths

- AEs leading to study drug dose adjustment/temporary interruption or permanent discontinuation
- AEs leading to study drug permanent discontinuation, including deaths
- AESIs leading to study drug permanent discontinuation with patients starting rescue medication(s) (ACEI/ARB)

AEs will be summarized as appropriate by presenting the number and percentage of patients reporting AEs by primary system organ class, by preferred term, by maximum severity, and by relationship to the investigational treatment.

In addition, the primary assessment for safety is the reporting of vital signs (i.e., sitting systolic blood pressure, sitting diastolic blood pressure, and heart rate) by visit with standard summary statistics (n, mean, standard deviation, minimum, Q1, median, Q3, maximum), including changes from baseline.

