SOLVD Investigators (1992) Effect of enalapril on mortality and the development of heart failure in asymptomatic patients with reduced left ventricular ejection fractions. *N Engl J Med*; 327:685-691.

13 Appendix 1: Clinically notable laboratory values

Clinically notable laboratory abnormalities for selected tests based on a percent change from baseline:

Hematology

RBC count	>50% increase, >20% decrease
Hemoglobin	>50% increase, >20% decrease
Hematocrit	>50% increase, >20% decrease
WBC count	>50% increase, >50% decrease
Platelet count	>75% increase, >50% decrease

Blood Chemistry

ALT (SGPT)	>150% increase
AST (SGOT)	>150% increase
BUN	>50% increase
Creatinine	>50% increase
Total bilirubin	>100% increase
CPK	>300% increase
Alkaline phosphatase	>100% increase
Sodium	>5% decrease
Potassium	>20% increase, >20% decrease
Uric acid	>50% increase

14 Appendix 2: Liver event and laboratory trigger definitions and follow-up requirements

Table 14-1 Liver event definitions

Definition/ threshold	
AE of special interest	
Laboratory values	ALT or AST > 3 x ULN ALP > 2 x ULN TBL > 1.5 x ULN
Medically significant event (SAE)	
Laboratory values	ALT or AST > 5 x ULN (with or without TBL > 2 x ULN [mainly conjugated fraction]) ALP > 5 x ULN (with or without TBL > 2 x ULN [mainly conjugated fraction]) TBL > 3 x ULN Potential Hy's Law cases (defined as ALT/AST > 3 x ULN and TBL > 2 x ULN [mainly conjugated fraction] without notable increase in ALP to > 2 x ULN)
AEs	Any clinical event of jaundice (or equivalent term) ALT or AST > 3 x ULN accompanied by general malaise, fatigue, abdominal pain, nausea, or vomiting, or rash with eosinophilia Any event that links to a preferred term (PT) in the MedDRA dictionary falling under the SMQ sub-module "Drug-related hepatic disorders – severe events only"** or any "Hy's law case" PT

* These events cover the following: hepatic failure, fibrosis and cirrhosis, and other liver damage-related conditions; the non-infectious hepatitis; the benign, malignant and unspecified liver neoplasms

Table 14-2 Liver event follow up requirements

Criteria	Event type	Actions required	Follow-up monitoring

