Potential Hy's Law case ^a	Medically significant	Discontinue the study drug immediately Hospitalize, if clinically appropriate Report to Novartis as an SAE Establish causality	ALT, AST, TBL, Alb, PT, ALP and γGT until resolution ^c (frequency at investigator discretion)
ALT or AST			
> 8 x ULN	Medically significant	Repeat LFT within 48 hours If elevation persists, discontinue the study drug immediately Hospitalize if clinically appropriate Report to Novartis as an SAE Establish causality	ALT, AST, TBL, Alb, PT, ALP and γGT until resolution ^c (frequency at investigator discretion)

Criteria	Event type	Actions required	Follow-up monitoring
> 5 to \leq 8 x ULN	Medically significant	Repeat LFT within 48 hours If elevation persists for more than 2 weeks , discontinue the study drug Report to Novartis as an SAE Establish causality	ALT, AST, TBL, Alb, PT, ALP and γ GT until resolution ^c (frequency at investigator discretion)
> 3 x ULN accompanied by symptoms ^b	Medically significant	Discontinue the study drug immediately Hospitalize if clinically appropriate Report to Novartis as an SAE Establish causality	ALT, AST, TBL, Alb, PT, ALP and γ GT until resolution ^c (frequency at investigator discretion)
> 3 to \leq 5 x ULN (patient is asymptomatic)	AESI	Laboratory to report to Investigator and Investigator to Novartis Repeat LFT once or twice in the week If elevation persists, establish causality	Investigator discretion Monitor LFT within 1 to 4 weeks or at next visit
\leq 3 x ULN (patient is asymptomatic)	N/A	Repeat LFT at next visit	
ALP (isolated)			
> 5 x ULN	Medically significant	Repeat LFT within 48 hours If elevation persists, report to Novartis as an SAE Establish causality	Investigator discretion Monitor LFT within 1 to 4 weeks or at next visit
> 2 to \leq 5 x ULN (patient is asymptomatic)	AESI	Laboratory to report to Investigator and Investigator to Novartis Repeat LFT once or twice in the week. If elevation persists, establish causality	Investigator discretion Monitor LFT within 1 to 4 weeks or at next visit
\leq 2 x ULN (patient is asymptomatic)	N/A	Repeat LFT at next visit	
TBL (isolated)			

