9.7.1.6.1 Adverse events

Any adverse events (AEs) occurred during the study period will be assessed, overall, by primary system organ class, by preferred term, by maximum severity, by relationship to the investigational drug according to the Medical Dictionary for Regulatory Activities (MedDRA).

The MedDRA version used for reporting the study will be described in a footnote.

Within each AE report, the following rules are applicable. If a subject reported more than one adverse events with the same preferred term, the adverse event with the greatest severity will be presented. If a subject reported more than one adverse event within the same primary system organ class, the subject will be counted only once with the greatest severity at the system organ class level, where applicable.

The number and percentage of subjects reporting the following AEs will be summarized by primary system organ class, preferred term.

- Overall AEs
- Serious adverse events (SAEs)
- AE of special interests (AESIs), i.e. AEs of hypotension, hyperkalemia or renal dysfunction
- Angioedema/angioedema-like events
- Deaths
- AEs leading to study drug dose adjustment/temporary interruption or permanent discontinuation
- AEs leading to study drug permanent discontinuation including deaths
- AESIs leading to study drug permanent discontinuation with patients starting rescue medication(s) (ACEI/ARB)

The most common adverse events reported ($\geq 1\%$ for each preferred term in the SOC-PT table) will be presented in descending frequency according to its incidence starting from the most common event.

For the legal requirements of ClinicalTrials.gov and EudraCT, two required tables on treatment emergent adverse events which are not serious adverse events with an incidence greater than 5% and on treatment emergent serious adverse events and SAE suspected to be related to study treatment will be provided by system organ class and preferred term on the safety set population.

If for a same patient, several consecutive AEs (irrespective of study treatment causality, seriousness and severity) occurred with the same SOC and PT:

- a single occurrence will be counted if there is ≤ 1 day gap between the end date of the preceding AE and the start date of the consecutive AE
- more than one occurrence will be counted if there is > 1 day gap between the end date of the preceding AE and the start date of the consecutive AE

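### The AESI definition used for analysis leaves out the liver-test elevations that the protocol itself designates as AESIs

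*SAP*

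**What the plan says.** Two parts of the plan define AESI, and they differ.

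**Safety monitoring.** Protocol 7.3 divides liver events into two categories, the first being "Liver events of special interest (AESI) which consist of LFTs elevations". Table 14-1 in Appendix 2 gives the thresholds under its special-interest heading: "ALT or AST > 3 x ULN ALP > 2 x ULN TBL > 1.5 x ULN". Table 14-2 types the matching asymptomatic ranges as AESI and requires notification of the sponsor: "Laboratory to report to Investigator and Investigator to Novartis". Liver follow-up information and procedures "should be recorded on appropriate CRF pages, including the liver event overview CRF pages".

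**Analysis.** Protocol 9.4 lists among the primary safety assessments "adverse events of special interest (AESI), i.e., hypotension, hyperkalemia, or renal dysfunction". SAP 9.7.1.6.1 repeats this as "AE of special interests (AESIs), i.e. AEs of hypotension, hyperkalemia or renal dysfunction" and summarizes it by system organ class and preferred term. SAP 9.7.1.8 repeats the primary-variable analysis by age group, sex and race.

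**Narratives.** The protocol summary and protocol 9.5.3 promise narratives for SAEs and AESIs. Neither place says which AESI definition applies.

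**The concern.** Safety and tolerability are the only objective of this study, and protocol 7.3 sets up its liver process to make the assessment of hepatotoxic potential more reliable. A programmer working from the SAP would select three conditions for the AESI summary. A narrative writer working from protocol 7.3 would add liver-test elevations. The two would pick different patients under the same label. A reader of the study report would see an AESI table with no liver events and could take that to mean that none of the protocol's liver AESIs occurred. What is at stake is the content of one primary safety summary, its subgroup repeats and the scope of the narratives. No hypothesis test or sample size is involved.

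**Working it through.** No arithmetic applies, so the check sets the passages side by side.

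| Place | What counts as an AESI | Liver included? |
|---|---|---|
| Protocol 7.3 | Liver-test elevations | Yes |
| Table 14-1 | ALT/AST > 3, ALP > 2, TBL > 1.5 x ULN | Yes |
| Table 14-2, AESI rows (asymptomatic) | ALT/AST > 3 to ≤ 5; ALP > 2 to ≤ 5; TBL > 1.5 to ≤ 3 x ULN | Yes |
| Protocol 9.4 | Hypotension, hyperkalemia, renal dysfunction | No |
| SAP 9.7.1.6.1 | Hypotension, hyperkalemia, renal dysfunction | No |
| Protocol summary and 9.5.3 (narratives) | AESIs, not defined there | Not stated |

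1. *Is it the same term?* The abbreviation list has a single entry for AESI. No passage separates AESIs for reporting from AESIs for analysis.

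2. *Is the analysis list closed?* Both protocol 9.4 and the SAP introduce it with i.e., which makes it a definition and not a set of examples. None of the three AESI rows of Table 14-2 falls under any of the three conditions.

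3. *Is there another liver output?* Angioedema has its own line beside the AESI line in both documents; liver events have none. SAP 9.7.1.6 limits the safety evaluation to adverse events and vital signs. SAP 9.7.1.3 mentions safety laboratory evaluation, but no laboratory output is described. Protocol 8.3 keeps local laboratory results out of the clinical database, so a laboratory table could not supply the missing group.

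4. *What still reaches an output?* A liver event recorded as an AE appears in the overall tables by system organ class and preferred term. Protocol 7.3 treats medically significant liver events as SAEs, so they reach the SAE summary and the narratives. If a recorded liver AE leads to a dose change or discontinuation, it also enters those AE summaries.

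5. *What changes?* The AESI summary and its subgroup repeats contain no liver events, and it is undecided whether non-serious liver AESIs get a narrative.

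6. *How many patients?* Neither document gives a rate for liver AESIs, so no count can be derived.

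**The case against.** The best defence is that the three-item list is deliberate. Protocol 3.6 names hyperkalemia, hypotension and renal impairment as its example risks. Sections 5.5.5, 5.5.6 and 5.5.9 tie dose adjustment and related guidance to the same three through Appendices 3 to 5. The SAP follows protocol 9.4 faithfully. Section 7.3 could be read as a follow-up and notification category and not an analysis class. The study is single-arm and descriptive, and scheduled liver tests after baseline fall only at Visits 5, 6 and 8. The MAP cited in SAP 9.7.1 is not available to us, and the text we have breaks off at the end of SAP 9.7.1.6.1 and in 9.8.

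Much of this stands. The SAP does not deviate from protocol 9.4, and a liver output specified elsewhere cannot be excluded. It does not remove the conflict: Table 14-1 uses the AE of special interest label itself, the narrative promise is unqualified, and the AESI line in the SAP does not refer to the MAP. If two concepts are intended, the plan has to say so.

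A reader might infer four stronger things that the documents do not support:

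- *That liver events go unreported.* They do not, for the reasons in step 4 of the check.
- *That AESI-tier elevations never entered as AEs will vanish.* All three AESI rows are limited to asymptomatic patients, and the AE-page rule in protocol 6.5.4 is worded narrowly ("If the laboratory abnormality induces clinical signs or symptoms, or requires therapeutic intervention, and satisfies the criteria defined in"). But protocol 7.1 makes a clinically significant or treated value an AE without symptoms, the Table 14-1 heading may itself prompt AE entry, and the liver CRF pages exist. The loss is possible but not shown, and changing the definition alone would not cure it.
- *That the closed list costs the reader a once-per-patient liver count.* The SAP specifies no such row per condition for the three named AESIs either.
- *That the summary of AESIs leading to discontinuation with rescue medication is materially affected.* No AESI-tier row in Table 14-2 directs discontinuation. Protocol 7.3 allows it where appropriate, so some effect cannot be ruled out, but little is likely to be lost.

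**Conclusion.** The definitions conflict, and the plan as written produces an AESI summary without a class that the protocol calls AESI. It also leaves the narrative scope for non-serious liver AESIs open. This should be corrected, but it is a modest defect: it concerns the grouping and labelling of events that, once recorded as AEs, are reported elsewhere, and its size in patients is unknown. The conclusion rests on reading i.e. as closing the list and on AESI having one meaning throughout the protocol. It would reduce to a missing cross-reference and a narrative-scope clarification if the MAP already provides a liver output.

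**What to change.** In SAP 9.7.1.6.1, add the liver events of protocol 7.3 and Appendix 2 to the AESI definition. Make the same change in protocol 9.4 if the protocol is amended again; otherwise record it in SAP 9.8 as a change from the planned analysis. Present these events as a liver grouping within the AESI summary. Because laboratory values are not in the database, build the grouping from recorded AEs and, where they identify cases, the liver event overview CRF pages. State that the same definition selects patients for the AESI narratives. If the project MAP already specifies a liver output, cite it in the SAP and still settle the narrative scope.

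The cost is a wording change, one extra grouping and some additional narratives. No new data collection is needed. The content of the liver CRF pages is not in the documents, so their use as a source is conditional; the grouping from recorded AEs does not depend on it.

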9.7.1.6.2 Vital Sign

Sitting systolic blood pressure, sitting diastolic blood pressure, and sitting pulse rate will be summarized by visit with standard summary statistics (n, mean, standard deviation, minimum, Q1, median, Q3, maximum), including changes from baseline. Baselines are defined in [Section 9.7.1.3](#). Graphical mean plots for these vital signs will also be provided.

The descriptive summaries will be presented by vital sign and visit. Change from baseline will only be summarized for subjects with both baseline and post-baseline values and will be calculated as:

- change from baseline = post-baseline value – baseline value

9.7.1.7 Analysis of the secondary variable

No secondary variable defined in this study.

9.7.1.8 Supportive analyses

For supportive purposes, the analysis of the primary variable described in [Section 9.7.1.6](#) will be applied in the following subgroups:

- Age group $<65, \geq 65$ years
- Age group $<75, \geq 75$ years
- Gender (male, female)
- Race (Caucasian, Black, Asian, Other)

9.7.2 Interim analyses

No interim analysis was planned.

9.7.3 Sample size calculation

All surviving patients randomized in PARADIGM-HF can be considered for eligibility in this open-label study (CLCZ696B2317). It is estimated that 5,000 patients (about 59% of the core study population and approximately 72% of surviving patients) will meet the eligibility criteria and be enrolled into this open-label trial; however, since there is only one treatment arm in the study and treatment-related statistical comparisons are not planned, a specific sample size for the study is not required.

9.8 Changes in the conduct of the study or planned analyses

The following changes from the planned analyses according to the study protocol were performed.
